## **A. Introduction**

During the first two years of the COVID-19 pandemic, the City of Chelsea, Massachusetts held a lottery to allocate cash benefits to its residents for ten months. In one of the original analyses of the Chelsea Eats program, the survey results showed that there was a higher rate of pregnancy in the treatment group compared to control. The underlying mechanism, however, remained unclear; the cash benefit could theoretically have induced changes in family planning or in maternal health, leading to the observed changes in pregnancy rates. Using data from the Chelsea Eats program, we propose to study the impact of the cash benefit on reproductive and perinatal health.

This proposal and analysis plan detail the intervention, randomization, and data source. Importantly, while this analysis plan is specified after the conduct of the trial, it does pre-specify the outcomes and statistical analysis prior to analysis of the data. No analyses of post-intervention outcomes were conducted prior to gaining access to the data.

## **B. Treatment**

Chelsea, Massachusetts, a city of 40,000 people just north of Boston, was among the places in the country hardest hit by COVID-19, both from a health and an economic perspective. Its heavily Latino population is concentrated in sectors of the economy that were shut down when the pandemic hit, and Chelsea residents are also disproportionately likely to be front-line service workers exposed to infection risk. In April 2020, local community organizations and the City of Chelsea responded to the economic crisis facing jobless Chelsea residents by mounting an unprecedented food distribution effort.

In September 2020, after five months of running its food distribution sites, the City redirected its efforts toward distributing financial support so that residents could purchase their own food through a program called Chelsea Eats. By combining city general revenue funds, state aid, and philanthropic contributions, the City assembled enough resources to distribute Chelsea Eats debit cards to approximately 2,000 households and to replenish the cards on a monthly basis for a total of six months, that was later extended to ten months. The card amounts vary with household size. Most households received \$400 per month, but one- and two-person households received \$200 and \$300, respectively. Spending from the cards was not restricted to food but could be spent on anything and anywhere Visa was accepted. In total, 3,615 households applied for the cards, and 2,074 were chosen to receive the cash assistance cards via a lottery. The debit cards were credited with the first payment on November 18th, 2020 and the second payment on December 18th, 2020. The program continued with monthly credits through August 2021.

### **C. Randomization and Participant Eligibility**

Between July 27, 2020 and August 17, 2020, the City accepted applications for the Chelsea Eats cash assistance cards. Multilingual information about the cards was distributed to individuals using the city-run food distribution sites. Additionally, information and applications were disseminated to community-based organizations, food pantries, faith groups, health care organizations, and low- and moderate-income housing complexes. Direct outreach to residents by city staff occurred in multiple locations, including food pantry lines, COVID-19 testing lines, and social service agencies. Applications could be submitted online via the city's website or on paper by dropping them off or mailing them to City Hall. In practice, most applications were submitted by residents attending one of the various city or community partner food pantries, where city staff, equipped with tablets, assisted residents with the application.

Eligibility criteria included:

- Resident of Chelsea, Massachusetts
- Household income at or below 30% of the U.S. Department of Housing and Urban Development's Area Median Income

The lottery was a weighted lottery. Specifically, a household could receive additional lottery tickets by meeting any of the following criteria:

- No one in the household was currently working
- The household was not receiving unemployment insurance
- The household was not receiving food assistance (e.g., SNAP benefits)
- There was a disabled household member
- There was a household member over 65 years of age
- There was a household member who was a veteran
- There was a household member who was under 6 years of age
- There was a household member between the ages of 6 and 17

The total number of lottery tickets per application ranged from 1 to 8. Although it was the city's intention to restrict households to a single application, some households managed to enter the lottery with more than one application. In these cases, the household still received only a single Chelsea Eats card. Records for the duplicate applicants will be combined into a single record, summing the lottery tickets across the duplicate records to determine the household's overall probability of winning the lottery. We account for the differential probability of winning the lottery across households in the statistical analysis (see section E.2).

Of note, some households never picked up their Chelsea Eats cards. The city then gave these unused cards to households from a randomly generated waitlist that was created at the time of random assignment. All waitlisted households ultimately received Chelsea Eats cards and are therefore part of the treatment group. The waitlist households received their cards approximately one month later than the primary lottery winners, but the cards were credited with both the payments for the first and second months – so the total payments received by waitlist households are the same as initial lottery winners.

## **D. Data, Outcomes, and Other Variables**

### *D.1. Data*

Female study participants of childbearing age (typically defined as age 15-44) will be matched to their electronic health record at Cambridge Health Alliance (CHA), Mass General Brigham (MGB), and East Boston Neighborhood Health Center (EBNHC) using a probabilistic algorithm based on name, date of birth, gender, address, and phone number.

### *D.2. Planned Outcomes*

Outcomes will be assessed on a per-participant basis and measured using the electronic health record data.

#### 1. Primary Outcome

##### a. Pregnancy

- i. We will first confirm the result from the survey data by assessing for pregnancies using the electronic health record data.
- ii. Pregnancies will be identified in the electronic health record as a positive urine or blood pregnancy test, ultrasound, and/or diagnosis codes over the 10 months of the trial.
- iii. We will then use the electronic health record identify live child births delivered vaginally or via Cesarean section. These can occur after the 10-month duration of trial.
- iv. Any pregnancy without an eventual delivery (not carried to term), the primary outcome for our main analysis, could be indicative of miscarriage, abortion, or fetal death, which will be assessed further with the secondary outcomes below.

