#### 2. Secondary Outcomes

##### a. Miscarriage

- i. We will use diagnosis codes and documentation within clinical notes to subsequently identify miscarriages that present to the health care setting.

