#### *E.4. Alternative specifications and sensitivity analyses*

Our primary specification includes patient characteristics and baseline values of the outcome in the model to improve power as well as any chance imbalance between the study arms after randomization. As described in section E.1., we will compare covariates between the treatment and control groups, and we will explore whether our results are sensitive to inclusion of these covariates in the model. Importantly, our primary specification accounts for differential probability of winning the lottery using inverse probability weights. As an alternative approach, we will include the set of covariates that are correlated with treatment probability into the model, specifically indicators for number of lottery tickets. Finally, as a sensitivity check, we will also conduct our analyses on the subpopulation of participants with established primary care at one of the clinical sites of care.

To ensure our estimates are robust to method of estimation, we will also estimate generalized linear models assuming a negative binomial distribution for the count utilization outcomes and a generalized linear model with a Bournoulli distribution and logit link function for the binary outcomes. In a final robustness check, we will Winsorize the utilization measures to ensure that our estimates are not sensitive to outliers.

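### Pregnancy is found only through recorded care contacts, so an arm difference in testing or care-seeking could look like an effect on pregnancy without delivery, and the plan does not measure that difference

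*Combined protocol and SAP*

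**What the plan says.** Section D.2, item 1.a.ii, defines the event: "Pregnancies will be identified in the electronic health record as a positive urine or blood pregnancy test, ultrasound, and/or diagnosis codes". The connective makes any one marker sufficient, including a single positive test, and the marker must fall within the trial's 10 months. Section D.1 limits the records to three health systems.

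Item 1.a.iv names the outcome analysed: "Any pregnancy without an eventual delivery (not carried to term), the primary outcome for our main analysis". It covers miscarriage, abortion and fetal death together, and refers to the secondary outcomes for further assessment. Deliveries have a longer window than pregnancies: "These can occur after the 10-month duration of trial".

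Dependence on contact is acknowledged for one secondary outcome. Item 2.a will "subsequently identify miscarriages that present to the health care setting". Item 2.b identifies induced abortions from procedures and prescriptions, using clinical notes to separate them from management of a loss.

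Two other provisions come close to the point. Section E.1 covers attrition and baseline balance. Section E.4 adds that "we will also conduct our analyses on the subpopulation of participants with established primary care at one of the clinical sites of care". No section compares pregnancy testing or care contact between arms after the lottery.

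**The concern.** The two kinds of pregnancy leave different traces. One that reaches delivery normally generates repeated contacts and a delivery record. One that ends early may leave a single test, or nothing. If the arms differ in how often women attend or are tested, recorded non-deliveries can differ while true losses are the same.

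The plan gives reason to take this seriously. The Introduction offers changes in family planning or maternal health as possible mechanisms. Section D.2, item 2.e, makes the number and timing of prenatal visits an outcome, though only for pregnancies that deliver. Sections E.2 and E.4 treat utilization as an outcome. A difference in contact after the lottery is therefore among the effects under study.

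At stake is what the main result can mean. The study aims to explain an earlier survey finding whose mechanism was unclear. A contrast that cannot separate a change in loss from a change in detection of loss does not settle that, and a null result could hide two effects that cancel.

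**Working it through.** The plan states no event rate, detection rate, sample size or power, so there is no figure of its own to reproduce. Everything below is an illustration.

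**Inputs**
- From section B: "In total, 3,615 households applied for the cards, and 2,074 were chosen to receive the cash assistance cards via a lottery". That leaves 3,615 − 2,074 = 1,541 households, a ratio of 2,074 / 1,541 = 1.346 to 1.
- From section E.5: two-sided 5% significance.
- Assumed: 10% of women pregnant in 10 months; 25% of those pregnancies not delivered; both equal in the two arms. Detection of non-delivered pregnancies is varied. Matched women: 1,000 to 3,000 in total, at the household ratio.

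**Step 1. Apparent effect when the true effect is nil**

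Recorded primary rate = pregnancy rate × non-delivered share × detection probability.

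| Detection, control vs cash | Control | Cash | Difference | Ratio |
|---|---|---|---|---|
| 50% vs 60% | 0.10 × 0.25 × 0.50 = 1.25% | 0.10 × 0.25 × 0.60 = 1.50% | 0.25 points | 1.20 |
| 70% vs 75% | 0.10 × 0.25 × 0.70 = 1.75% | 0.10 × 0.25 × 0.75 = 1.875% | 0.125 points | 1.07 |

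The first two factors cancel, so the apparent risk ratio is the ratio of detection probabilities. Equal detection gives 1.00, and lower detection in the cash arm reverses the direction.

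**Step 2. If only some non-deliveries depend on testing**

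Let a share s of non-deliveries depend on testing, with detection d_C and d_T, and let the rest be found with the same probability d_0 in both arms:

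ratio = [s·d_T + (1 − s)·d_0] / [s·d_C + (1 − s)·d_0]

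For s below 1 and d_T above d_C this lies between 1 and d_T / d_C. The values 1.20 and 1.07 are therefore upper limits for their detection pairs. The documents give no value for s.

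**Step 3. Effect on the false-positive rate**

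Normal approximation for two proportions, both tails summed, unweighted and unclustered, for 1,000 to 3,000 women:
- 1.25% vs 1.50%: 6.0% to 8.6%, against a nominal 5%.
- 1.75% vs 1.875%: 5.1% to 5.6%.
- Over a wider grid (6–10% pregnant, 30–40% not delivered): 5.6% to 11% at 50% vs 60% detection, and 8% to 28% at 50% vs 70%.

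**Step 4. Where the extra detections fall**

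A pregnancy must be identified within 10 months (about 43.5 weeks), but its delivery may come later. Earlier testing can therefore also bring in late-window pregnancies that go on to deliver. With 30–40% not delivered, and detection of non-delivered pregnancies rising from 50% to 55%, 60% or 70%, the share of extra detections that are primary events is:
- 100% if delivered pregnancies are detected equally (97% in each arm) and first records are no earlier;
- 49–86% if first records are one week earlier in the cash arm;
- 52–87% if delivered detection is 95% vs 97%, with no shift in timing;
- 19–75% with delivered detection of 90% vs 95%, a two-week shift, or both.

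In proportional terms non-delivered pregnancies still move more: 50% to 60% is a 20% relative rise, while 95% to 97% is 2.1% (0.97 / 0.95 = 1.021). The ratios in step 1 do not depend on this share.

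**The case against.** The strongest reply is that the plan already separates part of the signal. Miscarriage can be found from diagnosis codes and clinical notes without any earlier test, and abortions leave procedure or prescription records. Both are analysed by arm, so an excess in the primary outcome that appeared in neither would already point to unclassified, often test-only, events. The established-primary-care analysis may also narrow differences in access. All of this stands, and it is why the risk sits chiefly with early losses. But miscarriage remains limited to "miscarriages that present to the health care setting", a subgroup defined by established care can still differ by arm in contact after the lottery, and none of these analyses measures testing.

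A second reply is that the illustration is assumed and modest. That is correct. At 50% vs 60% detection the false-positive rate rises by a few points, and at 70% vs 75% it hardly moves.

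Three stronger readings are tempting and are not supported:
- A reader might infer that any testing difference falls almost wholly on the primary outcome. Step 4 shows that this needs equal detection of delivered pregnancies and no earlier first records. The documents establish neither.
- A reader might infer that an early loss is found only if a test was done in time. The definition also accepts ultrasound and diagnosis codes.
- A reader might infer that the fault is lack of blinding. The plan does not mention blinding; that households know they hold a card is an inference from the intervention. The route is cash changing care-seeking, which does not depend on knowledge of allocation.

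**Conclusion.** The point holds as an unmeasured risk of bias. Ascertainment of the primary outcome depends on contact, one positive test suffices, and no planned analysis would show whether testing or contact differed by arm. Any difference in detecting non-delivered pregnancies passes directly into the primary contrast: a ratio of 1.20 at 50% vs 60%, 1.07 at 70% vs 75%, and less if only some non-deliveries are affected.

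It would be wrong to conclude that the result is biased, or in which direction. The documents contain no detection or testing rates, and the figures rest wholly on assumed inputs. That the change falls mainly on non-deliveries is an expectation from how pregnancies come to be recorded; as a share of extra detections it is not a majority under every assumption tried. The point deserves action because the remedy is cheap and bears on what the main result can be said to show.

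**What to change.** Add to section D.2, item 1, and section E.4:

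1. Extract all pregnancy tests in the 10 months, positive and negative. With the E.2 model, compare by arm the share of women with at least one negative test and the share with any recorded care contact. Do not rely on the share with any test, because a true rise in conceptions raises it too. Pregnancy care also adds to care contact, so the negative-test comparison should carry more weight.
2. Beside the primary analysis, split the primary outcome into events supported only by a positive test and events supported by ultrasound, a pregnancy or loss diagnosis, or an abortion record. Estimate each by arm. State that the stricter version still needs a care contact, so it reduces the problem without removing it.
3. State before analysis that an arm difference confined to test-only events, together with an arm difference in negative tests or care contact, will be reported as compatible with differential detection and not as established evidence of an effect on pregnancy loss.

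The cost is SAP wording, one more field from the same records and a few regressions. The stricter version excludes some true very early losses, so it should accompany the primary analysis and not replace it. The rule in item 3 could also make the report cautious about a real rise in very early losses, which is why it should say compatible with differential detection and not attribute the difference to it.

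### The primary outcome has no look-back or washout, so a signal left from a pregnancy that ended just before the window can count as a pregnancy without delivery

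*Combined protocol and SAP*

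**What the plan says.** The primary outcome is built in three steps in section D.2, item 1.a.

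- **Pregnancy (1.a.ii).** "Pregnancies will be identified in the electronic health record as a positive urine or blood pregnancy test, ultrasound, and/or diagnosis codes". The time limit is the 10 trial months. The wording lets any one signal suffice. Ultrasound is not qualified by its finding, and no code list is given.
- **Live birth (1.a.iii).** Births are then sought in the record. On timing the plan says only: "These can occur after the 10-month duration of trial". There is no earliest date and no rule tying a birth to a particular signal.
- **Primary event (1.a.iv).** "Any pregnancy without an eventual delivery (not carried to term), the primary outcome for our main analysis". The event is a residual, a signal without a delivery. It needs no positive evidence of a loss or abortion.

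The opening of D.2 adds: "Outcomes will be assessed on a per-participant basis and measured using the electronic health record data". Pregnancy episodes are not defined. For dates, section B says "The debit cards were credited with the first payment on November 18th, 2020" and "The program continued with monthly credits through August 2021", which makes ten monthly credits. I take the window to open at the first payment; the plan does not say so outright.

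**The concern.** A pregnancy can leave traces in the record after it has ended: a test that is still positive, or a pregnancy-related code at a follow-up visit. Take a woman who delivers in October 2020 and has such a code entered in December 2020. She has a signal in the window and no later delivery, so the rule as written makes her a primary event. A residual positive test after a loss in early November does the same. So can an isolated false-positive test or a mis-entered code, when no delivery follows.

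These errors would be few against all pregnancies, but they collect in the much smaller group without a delivery. That group is the only primary outcome, and it is meant to help explain a survey finding whose mechanism section A calls unclear.

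**Working it through.** **1. Does another section close the gap?**

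- Note review is planned for miscarriage and abortion (D.2, items 2.a and 2.b). It is not planned for confirming that a signal marks a new pregnancy.
- A timing rule relative to pregnancy is written for prenatal vitamins (item 2.c), but none for the primary outcome.
- Baseline values of the outcome enter as covariates (E.2). That adjusts the model and leaves false events in the outcome.

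No section gives a look-back, a washout, gestational-age dating or an episode rule.

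**2. How large could carry-over be?** The plan states no event rate or sample size, so there is no figure to reproduce. All inputs in this step are assumptions.

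*Range.* Let B/L be births per pregnancy not delivered, w the weeks a signal can persist, and q the chance that it is recorded in the window. Ten months are 10 × 30.4375 / 7 = 43.5 weeks.

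False events per true event: r = (B/L + 1) × (w / 43.5) × q. False share of events = r / (1 + r).

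| Case | B/L | w | q | r | False share |
|---|---|---|---|---|---|
| Low | 1 | 4 | 0.10 | 0.018 | 2% |
| Mid | 2 | 6 | 0.25 | 0.103 | 9% |
| High | 3 | 8 | 0.50 | 0.368 | 27% |

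*Upper bound.* Assume 60 births per 1,000 women a year and 25% of recorded pregnancies lost, which gives 20 losses per 1,000. Assume signals last 8 weeks after a birth and 6 weeks after a loss.

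- Women at risk of carry-over: 0.060 × 8/52 + 0.020 × 6/52 = 1.15%.
- True losses in 10 months: 0.020 × 10/12 = 1.67%.
- If a fraction f of those at risk leaves a signal in the window, the false share is 1.15f / (1.15f + 1.67). That is 15%, 26% and 41% for f = 0.25, 0.5 and 1. The shares do not depend on the birth rate, because both terms scale with it.

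**3. What does it do to the comparison?** Section B says: "In total, 3,615 households applied for the cards, and 2,074 were chosen to receive the cash assistance cards via a lottery". That leaves 1,541 households, a ratio of 2,074/1,541 = 1.346. Assume 600 control women, true risks of 3% (control) and 6% (cash), and the same false-event probability e in both arms. Each observed risk is p + (1 − p)e, so the risk difference becomes 0.03 × (1 − e). Power uses the normal approximation for two proportions at two-sided 0.05, ignoring weights and clustering.

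| e | Risk difference (points) | Risk ratio | Power |
|---|---|---|---|
| 0 | 3.00 | 2.00 | 76% |
| 0.5% | 2.985 | 1.86 | 71% |
| 1% | 2.97 | 1.75 | 67% |
| 2% | 2.94 | 1.60 | 60% |

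To link steps 2 and 3, multiply r by the 3% control risk. The mid case gives e of about 0.103 × 3% = 0.3%, the high case 0.368 × 3% = 1.1%, and the upper bound (1.15/1.67 = 0.69) about 2.1%. The mid case therefore lies above the 0.5% row of the table, with a power loss of less than five points.

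**The case against.** **Births inside the window.** A reader might infer that a postpartum code after an in-window birth also creates a false event. The documents do not support that. Outcomes are assessed per participant and the birth search has no earliest date, so such a woman most naturally counts as pregnant with a delivery. A woman with an in-window loss is already a true event, and her later signals add nothing.

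**A false excess of loss in the cash arm.** This too is tempting, but it needs signals that rise with births, tests or visits under treatment. Section A reports a higher pregnancy rate in the survey and no excess of births or contacts. Carry-over stems from pregnancies that ended before any cash was paid. The lottery balances these in expectation once the E.2 weights are applied. Cash could still change whether a follow-up visit is made and recorded; this is possible but not shown.

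**Every stray signal becomes an event.** It does not. A woman with a false signal can later conceive and deliver, and no upper limit is set on the delivery date.

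**Codes and size.** Without a code list, it is not known that postpartum codes would count, and every rate above is assumed. Both points are fair. They limit the size of the problem, but the missing look-back remains, and a residual positive test needs no code.

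**Conclusion.** The gap is real and narrow. Followed literally, items 1.a.ii and 1.a.iv can turn a signal from a pregnancy that ended shortly before 18 November 2020 into a primary event, and no section prevents it.

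The carry-over share is about 2% to 27% of primary events, with a mid case of about 9%. About 41% is a ceiling that requires every recently ended pregnancy to leave a signal, and it is tied to the 8- and 6-week persistence times. Stray false positives and coding errors would add an amount that cannot be judged from the documents.

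The harm to expect is noise, a smaller relative effect and lower power. The E.2 coefficient is a difference in means and hardly moves; the logit check in E.4 works on a relative scale and would show the attenuation. Nothing in the documents supports reading this as a source of a spurious treatment effect.

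**What to change.** In D.2, item 1.a.ii:

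1. Look back before the window for any birth, miscarriage or abortion. Ignore pregnancy signals within a fixed washout after it (for example 8 weeks), unless an ultrasound or a documented gestational age shows a new pregnancy.
2. Write down the code list and leave out postpartum and post-loss follow-up codes.
3. State that a delivery inside the window is credited to the same pregnancy.

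Add two sensitivity analyses to E.4: the plan's present single-signal definition, and a definition that requires a confirming second signal or note. The second should not be the main definition, because it can drop true early losses seen only once and makes counting depend on how often a woman attends.

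The cost is SAP wording, a code list and a look-back in records that are to be matched anyway. The main definition will miss a few quick re-conceptions; the single-signal analysis keeps them.

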##### b. Abortion

- i. We will also identify procedural abortions and prescriptions for medical abortions. Using documentation within clinical notes to distinguish between miscarriage-related abortions (i.e., those performed after early pregnancy loss, incomplete abortions, and ectopic pregnancies) and induced abortions, this outcome will focus specifically on induced abortions.

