##### c. Prenatal vitamin prescriptions prior to pregnancy

- i. To characterize family planning among participants, we will assess new use of prenatal vitamins, including multivitamins. Physicians can prescribe these vitamins or document over-the-counter use of them in

the electronic health record. We will exclude those that were prescribed or documented during pregnancy and focus specifically on those that occurred prior to any pregnancy over the 10 months of the trial.

- d. Contraception
  - i. To further understand family planning among participants, we will assess utilization of long-acting reversible contraceptive methods (intrauterine devices or implants) and prescriptions for hormonal birth control methods (pill, patch, ring).
- e. Number and timing of prenatal visits before delivery
  - i. In addition to quantity of visits, we will also assess for initiation during the first trimester and calculate the Adequacy of Prenatal Care Utilization (APNCU) Index, which characterizes the adequacy of a patient's prenatal care as inadequate, intermediate, adequate, or adequate plus based on the timing of their prenatal care initiation and the number of prenatal visits after initiation.
- f. Composite of birth outcomes
  - i. Following McConnell et al. (2022), we will construct a composite of at least one of: low birth weight, preterm birth, small for gestational age, or perinatal mortality. These are described in further detail below.
  - ii. *Birth weight* is a continuous measure of the infant's birth weight in grams. *Low birth weight* is defined as a birth weight less than 2500 grams.
  - iii. *Gestational age* at birth is a continuous measure of the infant's gestational age at birth. *Preterm birth* is defined as an infant born before a gestational age of 37 weeks.
  - iv. *Birth weight for gestational age* is a continuous measure of the infant's birth weight relative to the average in the population for a given gestational age at birth. *Small for gestational age* is defined as a birth weight below the 10th percentile for infants of the same gestational age.
  - v. *Perinatal mortality* is a binary indicator for whether there was a fetal death at or after 20 weeks of gestation or mortality within the first 7 days of life.

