### D.3. Patient Characteristics

The data includes information on participants' household size, disability status, veteran status, work status, income, receipt of other benefits or assistance, and utilization/spending prior to randomization. These characteristics come from the lottery application form or electronic health records and are assessed prior to randomization. In the event that there are high levels of missingness for any key covariate (i.e., >2%), multiple imputation methods will be used.

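### The primary outcome counts a pregnancy as an event when its delivery is missing from three systems' records, and the plan does not separate or report pregnancies with no recorded outcome

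*Combined protocol and SAP*

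**What the plan says.** Section D.1 has participants "matched to their electronic health record at Cambridge Health Alliance (CHA), Mass General Brigham (MGB), and East Boston Neighborhood Health Center (EBNHC") by a probabilistic algorithm. No other source of births is named. Section D.2 opens with "Outcomes will be assessed on a per-participant basis and measured using the electronic health record data".

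Under D.2, 1.a, a pregnancy is found through a test, an ultrasound or a diagnosis code during the ten trial months (item ii). Deliveries come next: "We will then use the electronic health record identify live child births delivered vaginally or via Cesarean section" (item iii). These may fall after the ten months, and no closing date is given. Item iv defines the event: "Any pregnancy without an eventual delivery (not carried to term), the primary outcome for our main analysis". It adds that such a pregnancy may point to miscarriage, abortion or fetal death, and leaves the breakdown to the secondary outcomes.

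Those outcomes supply most of the loss categories:

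- Miscarriage (2.a): "We will use diagnosis codes and documentation within clinical notes to subsequently identify miscarriages that present to the health care setting".
- Abortion (2.b): "this outcome will focus specifically on induced abortions". Ectopic pregnancy is mentioned only to set it apart from these.
- Perinatal mortality (2.f.v): includes whether "there was a fetal death at or after 20 weeks of gestation", but inside a composite.

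Three provisions come near the point. D.3 provides multiple imputation for "high levels of missingness for any key covariate", so it does not reach outcomes. E.1 checks attrition and balance by arm. E.4 repeats the analyses in participants with established primary care at a site.

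**The concern.** The event is the absence of a record, and no positive evidence of a loss is required. Three kinds of pregnancy can show neither a delivery nor a loss: one delivered where none of the three systems recorded it, one lost without reaching care, and one that was a false signal. All three count as events, and no planned table shows how many there are in each arm.

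The denominator is women, not pregnancies. If cash leads to more births, a fixed share of unrecorded births produces more events in the treatment arm, even when capture is the same in both arms. Section A makes this a live possibility: the survey found a higher pregnancy rate in the treatment group, and explaining that finding is the purpose of the study. An increase in births could then be read as an increase in pregnancy loss. If capture differs by arm, a false difference can go either way.

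A smaller point of wording: the parenthesis in the definition can be read to include preterm live births, which item iii counts as births.

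**Working it through.** The plan gives no event rate, effect size or sample size, so there is no figure of its own to reproduce. **Every input below is assumed**, and each woman is taken to have at most one pregnancy in the window.

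**Set-up.** Let *L* be true losses per woman, *D* deliveries per woman and *q* the share of deliveries unrecorded. The recorded event rate in an arm is *L + Dq*. Base case: 10% pregnant, 25% of those truly undelivered, so *L* = 0.10 × 0.25 = 0.025 and *D* = 0.10 × 0.75 = 0.075.

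**Share of events that are unrecorded deliveries**, *Dq/(L + Dq)*:

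- *q* = 5%: 0.00375/0.02875 = 13%
- *q* = 10%: 0.0075/0.0325 = 23%
- *q* = 20%: 0.015/0.040 = 37.5%

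With 20–35% undelivered, the share runs from 8.5% (0.0325/0.3825) to 44% (0.16/0.36).

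**Deliveries rise by a fraction *g*, losses unchanged, capture equal** (true difference 0). The observed difference is *gDq*, in percentage points:

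| *g* | *q* = 5% | *q* = 10% | *q* = 20% |
|---|---|---|---|
| 10% | 0.04 | 0.075 | 0.15 |
| 25% | 0.09 | 0.19 | 0.375 |
| 50% | 0.19 | 0.375 | 0.75 |

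With 5–15% pregnant and 20–35% undelivered, the range is 0.02 (0.10 × 0.0325 × 0.05) to 1.20 points (0.50 × 0.12 × 0.20).

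**No true effect, 20% v 10% of deliveries unrecorded by arm.** The difference is 0.075 × 0.10 = 0.75 points (0.33 to 1.20 over the same ranges). Its sign depends on which arm is captured less well.

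**Losses and deliveries both up 50%.** The true difference is 0.5 × 0.025 = 1.25 points. The observed difference is 0.5(*L + Dq*) = 1.44, 1.63 and 2.00 points. The sign is right and the size inflated.

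**Can the primary coefficient be split?** Write the primary indicator as *Y = Y₁ + Y₂*, with *Y₁* a documented loss and *Y₂* outcome not observed, mutually exclusive. A weighted least-squares coefficient is linear in the outcome. With the same covariates and weights, the CASH coefficients for *Y₁* and *Y₂* therefore add up to the one for *Y*. Taking 60–80% of losses as documented, equally in both arms:

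| Scenario | Documented loss | Not observed | Primary |
|---|---|---|---|
| Deliveries +50% only | 0 | 0.19 to 0.75 | 0.19 to 0.75 |
| Losses +50% only | 0.75 to 1.00 | 0.50 to 0.25 | 1.25 |
| Unequal delivery capture only | 0 | ±0.75 | ±0.75 |

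The split shows where an effect sits, which the primary coefficient alone cannot.

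**The case against.** **The plan does classify these pregnancies.** A reader might infer that the rule is absent. It is not: item iv makes any pregnancy without a delivery an event, so the unresolved ones are events by default. The weakness is what that rule absorbs and the lack of any separate count.

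**The plan is cautious about meaning.** Item iv says only that non-delivery may point to loss, and the secondary outcomes by arm would reveal much of the remainder. This is fair. They would not give it exactly, because fetal death sits inside a composite and ectopic pregnancy has no category.

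**The bias may be small.** For delivery increases of 10–25% the base-case bias is 0.04 to 0.375 points. If 500 to 3,000 women were analysed (an assumption), with a 3.25% event rate and the 57/43 split implied by 2,074 of 3,615 households, the unweighted, unclustered standard error would be about 1.6 to 0.65 points. Most of the tabulated values lie below one standard error. Nor do the documents suggest a mechanism for doubling non-capture in one arm. These points limit the severity, but without the count no reader can tell whether they apply.

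**Comparing ratios would mislead.** It is tempting to compare the primary and documented-loss results relative to their control means. With losses up 50% and deliveries unchanged, the primary difference is exactly the true 1.25 points. Its ratio, however, is 1.43, 1.38 or 1.31 at 5%, 10% or 20% unrecorded, against 1.5 for documented losses. A ratio check would flag a correct estimate, so the comparison belongs on the plan's difference scale. On that scale, false signals at an equal rate in both arms mainly add variance.

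**Existing checks.** E.1 and E.4 help in part. Neither isolates pregnancies without a recorded outcome, and primary care at a site does not ensure that a delivery is recorded there.

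**Conclusion.** The concern holds as a weakness in how the sole primary outcome can be interpreted, and it should be fixed before analysis. The rule in item iv counts unrecorded deliveries as events. On a per-participant difference it can show a false rise in pregnancy loss if cash raises deliveries, even with equal capture, or a false difference in either direction if capture differs by arm.

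A reader might go further and conclude that the primary result will be biased upwards, or that the outcome is invalid. The documents support neither. They give no pregnancy rate, no loss rate, no capture rate and no size for the survey finding, so the size and direction of any bias cannot be derived, and capture may prove good. The supported conclusion is narrower: the plan would not let a reader tell a change in losses from a change in unrecorded births.

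**What to change.** In D.2, 1.a.iv, keep the primary definition, its single test and its alpha, and add:

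1. A delivery documented anywhere in the three records, including one at an outside hospital, counts as a delivery.
2. Each remaining pregnancy is classed as a documented loss (miscarriage, induced abortion, ectopic pregnancy or fetal death) or as *outcome not observed*.
3. Participants with a primary event get two mutually exclusive indicators, with documented loss taking precedence. Fit the E.2 model to each with the same weights and covariates as the primary model, including the primary outcome's own baseline value, so that the coefficients add up. Report both CASH coefficients and the counts by arm.
4. The primary result is described as an effect on pregnancy loss only as far as the documented-loss component supports it. State that the other component may be unrecorded deliveries, unrecorded losses or false pregnancy signals.
5. Replace the parenthesis in the definition with *not ending in live birth*, to match item iii.

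The cost is protocol and SAP wording, one added analysis and some extra note review, since note review is already planned for miscarriage and abortion. The primary test and its power are unchanged.

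The added analysis has limits. It misses losses that never reached these systems and is biased if documentation differs by arm. With no effect on losses, 80% v 60% documented gives 0.025 × 0.20 = 0.50 points on documented losses, while deliveries up 50% with 10% unrecorded gives 0.375 points on the primary. If the arm with more deliveries is also the better documented, both errors point the same way. The two analyses are therefore not bounds, and the report should say so.
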